## **3.0 STUDY DESIGN**

This is a prospective, single institution, controlled, pilot study of patients admitted to the 7W ICU which will compare the incidence and delirium rates among patients undergoing routine care before

intervention (no routine psychiatric involvement) (control group) and patients after the intervention (psychiatry team rounding with the ICU team daily) (intervention group) . Randomization is not possible for this study; although block randomization was considered, it will result in sub-optimal data subject to bias.

A sample size of 104 (52 per group) is targeted based on an *a priori* sample size calculation. Patients will be screened on a daily basis for study eligibility by study personnel and ICU team members, before delirium develops. Patients in both groups will be given an information sheet, verbal consent will be obtained, and the patient's agreement to participate will be documented in the medical record. For patients who are unable to make their own decisions, the information sheet will be given to their designated healthcare decision maker, verbal consent will be obtained, and the healthcare decision maker's agreement will be documented in the medical record.

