## **6.0 STRATIFICATION/DESCRIPTIVE FACTORS/RANDOMIZATION SCHEME**

This is a prospective, single institution, controlled, pilot study of patients admitted to the 7W ICU. A sample size of 104 (52 per group) is targeted. Patients will be screened for study eligibility on a daily basis. The control group will undergo standard ICU care, which includes the use of the ABCDEF bundle (Appendix 1) daily, which involves delirium screening using the CAM-ICU tool (Appendix 2), but will not have routine psychiatric involvement in care. Enrollment and data collection will continue for as long as it takes to reach the target sample size of 52 patients for this group. We will then proceed to enroll patients into the intervention group, who undergo standard care (including ABCDEF bundle implementation, which is standard practice in 7W ICU) in addition to a psychiatric team intervention, which entails having a member of the psychiatric team (attending, resident, and/or fellow) participate in daily (Monday-Friday) multidisciplinary rounds with the ICU team; they will help provide nonpharmacological and pharmacological intervention strategies in patients diagnosed with delirium and help distinguish delirium from other psychiatric disorders which may be missed by the ICU team and provide earlier treatment of these conditions. This study phase will continue until the target sample size of 52 patients is reached.

Data will be collected for both the control and intervention groups (see Section 12) and compared.

Randomization is not possible for this study; although block randomization was considered, it will result in sub-optimal data subject to bias.

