## **12. DATA COLLECTION AND MONITORING**

Data which will be collected includes: age, gender, body mass index, history or alcohol or substance abuse, admitting diagnosis, dementia, comorbid conditions, admitting Sequential Organ Failure Assessment (SOFA) score, deliriogenic medications used during study enrollment, the interventions/medications used to treat delirium as designated by psychiatry in conjunction with the ICU team (in intervention group) and the ICU team (control group), and the number of days from ICU admission to study enrollment. Data on the incidence of ICU delirium, duration of delirium/mechanical ventilation, in-house mortality, and length of stay will also be collected.

Data will be collected using RedCap, a password protected website. No patient identifiers will be used. A copy of the information sheet will be provided to the patient and be placed in the patient's chart. We will retain a copy of the information sheet in a double locked storage office.

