characteristics between the 2 groups. The incidence of delirium will be compared using  $\chi^2$  test and multivariable logistic regression. Differences in the duration of delirium and MV between the intervention and control groups will be analyzed by analysis of variance (ANOVA). The length of stay will be compared by truncated negative binomial regression, while mortality rates will be compared via logistic regression. A sensitivity analysis will be performed in order to assess the possible confounding effect of the non-randomized nature of our study design. A propensity score model for receipt of standard care vs. psychiatric involvement will be performed in order to approximate a balanced covariate distribution between the 2 groups as that would be expected by randomization. We will then use the propensity score for each subject to perform an inverse probability weighted comparison of the groups on our trial outcomes.

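### In a non-randomised before/after comparison, Section 13.0 does not make a covariate-adjusted analysis lead, so measured case-mix differences between phases can bias the estimates meant to plan the next trial

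*Combined protocol and SAP*

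**What the plan says.** Allocation is by calendar phase. Section 3.0 states: "Randomization is not possible for this study; although block randomization was considered, it will result in sub-optimal data subject to bias". Section 6.0 describes filling the control group to 52 patients and continues: "We will then proceed to enroll patients into the intervention group".

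Section 13.0 then assigns the analyses:

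- **Delirium incidence (primary):** a chi-square "test and multivariable logistic regression". Neither is ranked above the other, and no covariates are listed.
- **Duration of delirium and of ventilation:** "Differences in the duration of delirium and MV between the intervention and control groups will be analyzed by analysis of variance (ANOVA".
- **Length of stay and mortality:** "The length of stay will be compared by truncated negative binomial regression, while mortality rates will be compared via logistic regression". No covariates are named.
- **Confounding:** "A sensitivity analysis will be performed in order to assess the possible confounding effect of the non-randomized nature of our study design". A propensity score is to be estimated and used to "perform an inverse probability weighted comparison of the groups on our trial outcomes". The covariates of the propensity model are not listed.

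Section 12 already collects suitable predictors: "age, gender, body mass index, history or alcohol or substance abuse, admitting diagnosis, dementia, comorbid conditions", followed by the admitting SOFA score and, later in the same list, the days from ICU admission to enrolment.

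**The concern.** Without randomisation, nothing makes the two cohorts alike in age, severity or time already spent in the ICU. A two-group comparison attributes any such difference to psychiatry rounding. Section 13.0 recognises this risk, but for the secondary outcomes it places the only stated remedy in a sensitivity analysis. For the primary outcome, a reader cannot tell which result governs if the chi-square and the logistic model disagree.

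The stakes are mainly about estimation. Section 13.0 says the effect size and base rate from this pilot will be used to design larger multi-centre studies. A case-mix shift in the leading estimate would carry into that trial's sample size.

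**Working it through.** **1. The plan's own figures.** The inputs from Section 13.0 are a 40% base rate, a 25-point reduction (to 15%) and 47 per group. The text says 25%; the stated interval shows that points are meant.

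Difference: 0.25 ± 1.96 × √(0.40×0.60/47 + 0.15×0.85/47) = 0.25 ± 0.173, or 7.7% to 42.3%. The plan states 8%–42%, so this reproduces. The exact (Clopper-Pearson) interval for 40% of 47 is 26.0% to 55.3%, against the stated 26%–55%. Both are intervals for unadjusted proportions and make no allowance for case-mix.

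**2. Effect of a systematic case-mix shift on delirium.** These inputs are assumptions, not from the documents: age and SOFA are independent and standardised, with log-odds per SD of 0.5 and 0.6. The model is logit(p) = b₀ + 0.5·age + 0.6·SOFA, with b₀ set so that the average risk is the plan's 40% (b₀ ≈ −0.46). There is no true group effect. One cohort's mean is moved by the same amount on both covariates. Marginal risks come from averaging over 400,000 draws, and rejection rates from several simulation runs of 2,000 to 4,000 trials with 47 per group.

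| Shift on both | Crude difference | Crude test rejects | Adjusted logistic rejects |
|---|---|---|---|
| 0 | 0 | 4–5% | about 5% |
| 0.2 SD | 4.7 points | 6–7% | 4–5% |
| 0.3 SD | 7.1 points | 9–11% | about 5% |
| 0.4 SD | 9.6 points | 14–16% | about 5% |

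Against the 25-point planning effect, the bias is 4.7/25 = 19% to 9.6/25 = 38%. Against the 17.3-point half-width from step 1, it is 27% to 55%.

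**3. A simpler cross-check, which also covers ANOVA.** Assume one binary risk factor with delirium risk 55% if present and 25% if absent, and a prevalence differing by 20 points between phases. The crude bias is 0.20 × (0.55 − 0.25) = 6 points. In 4,000 null trials the chi-square rejected in 9.0% and the adjusted logistic model in 4.8%. If the same factor moves a continuous outcome by 1 SD, the bias is 0.20 SD; two-group ANOVA rejected in 13.5% and the adjusted linear model in 5.1%. With risks of 50%/30% or 60%/20%, the 20-point imbalance gives 4 or 8 points of bias and a chi-square error of about 6.8% or 12.3%.

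**4. How many covariates the data can carry.**

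- Delirium at the planning rates: 47 × 0.40 + 47 × 0.15 = 18.8 + 7.05 ≈ 26 events. Group plus three covariates leaves 26/4 = 6.5 events per parameter; group plus two leaves 26/3 ≈ 8.7.
- Mortality: the documents give no planning rate. If 14% die (an assumption), 0.14 × 94 ≈ 13 deaths. Group plus three covariates leaves 13/4 ≈ 3 per parameter; group plus one leaves 13/2 = 6.5.

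**5. What adjustment does to precision.** In the step 2 model with no shift, the median standard error of the group log-odds ratio rises from about 0.42 (crude) to about 0.46 (adjusted). At a 0.4 SD shift it rises from about 0.42 to 0.47.

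**The case against.** The strongest reply is that adjustment is already planned. The primary outcome has a multivariable model, and inverse probability weighting covers all trial outcomes, expressly because of the non-randomised design. With unadjusted and weighted results side by side, measured confounding would be visible. This stands: a reader might infer that the plan ignores confounding, and it does not. What remains is rank. Nothing says which primary analysis decides, and for the secondary outcomes the only stated adjustment is labelled a sensitivity analysis.

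A reader might also infer that every secondary analysis is crude. The text does not go that far. Only the ANOVA is an unadjusted two-group comparison on its face. The length-of-stay and mortality regressions could carry covariates. That they do not is an inference from the silence and from the word multivariable being used only for the primary.

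Three further inferences should be resisted:

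- **That adjustment will tighten the interval.** For log-odds ratios it does the opposite (step 5).
- **That chance imbalance at 47 per group shows bias.** It does not, because the crude test's 5% level already allows for it (the zero-shift row of the table). Bias needs a systematic shift between phases.
- **That 14–16% is the expected error rate.** It belongs to an assumed 0.4 SD shift on both covariates in the same direction, and the documents give no figure for any shift.

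Finally, this is a pilot with no stated alpha or power, so the rejection rates carry less weight than the bias in the estimate. That is fair. The bias still matters because estimation is the stated purpose.

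**Conclusion.** The point holds in a limited form, as a cheap improvement. Section 13.0 compares consecutive cohorts by unadjusted ANOVA for the two durations and by regressions with no stated covariates for length of stay and mortality. For the primary outcome it leaves a crude and an adjusted analysis unranked. Measured case-mix differences can therefore bias the leading estimates.

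Under the assumed covariate effects, a systematic shift of 0.2 to 0.4 SD on both age and SOFA is worth about 5 to 10 points of delirium incidence. Including those covariates keeps null rejection near 5%. These sizes rest on the assumed log-odds, on a systematic shift existing, and on the adjustment model being right.

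Adjustment deals with measured case-mix only. It does not remove changes in care, staffing or recording between the two calendar phases, and the write-up of results should say so.

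**What to change.** In Section 13.0:

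1. State that the covariate-adjusted logistic model is the primary analysis of delirium incidence and that the chi-square is descriptive.
2. Name a short baseline set in advance: age and admitting SOFA, with days from ICU admission to enrolment added if the number of events allows.
3. Replace ANOVA with linear regression on group plus that set, for both duration outcomes.
4. Put the same covariates in the length-of-stay model.
5. For mortality, choose one in advance: a model with at most one covariate such as SOFA, a penalised model, or the planned weighted estimate as the lead. The propensity model predicts group, with about 47 patients on each side, so the number of deaths does not limit it.
6. Otherwise keep inverse probability weighting as the sensitivity analysis, and list the covariates of its propensity model.

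If the sponsor already intended covariates in the length-of-stay and mortality models, naming them is enough for those two.

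The cost is SAP wording and a few lines of code; no new data are needed. The statistical price is a slightly larger standard error for the odds ratio (about 0.42 to 0.46 in the illustration) and a covariate list that must stay short with about 26 delirium events.

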## **1.0 BACKGROUND AND HYPOTHESIS**

We are interested in evaluating a multifaceted prevention protocol for ICU delirium. Delirium affects 45-80% of elderly ICU patients, 60-80% of mechanically ventilated ICU patients, and 20-50% of non-mechanically ventilated ICU patients (1-4). About 30-40% of cases are preventable (1, 2). Without routine screening, delirium is often undiagnosed (5-7). Numerous studies have consistently shown that ICU delirium is associated with a worse prognosis (8). The annual cost of delirium and its ramifications in the U.S., is estimated to be \$4-16 billion (1).

Delirium impacts emotional well-being, as delirious patients experienced delusional memories and had less factual recall than non-delirious patients (9-11). A meta-analysis performed by Zhang et al. found delirium to be associated with a higher mortality rate, longer ICU and hospital lengths of stay, longer duration of mechanical ventilation, and higher probability of discharge to a skilled placement facility. (9) ICU-acquired delirium is independently associated with increased cognitive and physical impairment and health care costs (6, 12). Delirium was also found to be associated with more complications (9,13). Patients who develop delirium have a 2-3 times increased risk of dying during ICU admission (8, 14), with ICU mortality ranging from 1-16% (15-17), and an in-hospital mortality rate of 25% to 33%. (12, 18). It is also associated with increased hospital length of stay (13, 19) and each additional day of delirium increases post-discharge mortality up to a year after discharge (14, 16, 19).

Patients with ICU delirium had a higher incidence of cognitive impairment at hospital discharge, and up to 18 months post-discharge (20, 21) A longer duration of delirium in the hospital was associated with worse global cognition and executive function scores at 3 and 12 months (22), and it is associated with the development of new-onset dementia, or worsening of existing dementia (2, 22). In addition to cognitive problems, delirium was found to be associated with more problems in activities of daily living and worse scores on sensorimotor function tests at follow-up (3). Anxiety, depression, and posttraumatic stress disorder are common in survivors of critical illness (20, 21).

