## **2.0 OBJECTIVES AND PURPOSE**

The purpose of our study is to determine the effect of delirium prevention care bundle protocols, and a multi-disciplinary care model rounding with a psychiatry team (intervention group) on ICU delirium and patient outcomes as compared to a group undergoing standard care without routine psychiatry team participating in ICU rounds (control group). Since the incidence of ICU delirium is so high and it has negative ramifications on patient survival, long-term outcomes, cognitive function, and places a heavy burden on the healthcare system and cost, preventative strategies are desperately needed. Using bundle care protocols and multidisciplinary rounding with psychiatry may be a feasible and cheap measure to help prevent delirium in ICU patients.

The primary objective is the incidence of ICU delirium.

The secondary objectives are:

- duration of delirium
- ICU and hospital length of stay
- days of mechanical ventilation (if applicable)
- in-hospital mortality

Our primary hypothesis is that the intervention of psychiatry team participation in multidisciplinary ICU rounds with the surgical ICU team will result in a decreased incidence of delirium compared to standard care without routine psychiatry team involvement. Our secondary hypothesis is that psychiatric team participation in multidisciplinary ICU rounds will decrease delirium duration, decrease ICU and hospital length of stay, decrease mechanical ventilation duration, and decrease in-hospital mortality compared to the standard care group.

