## **9.0 CLINICAL AND LABORATORY EVALUATIONS AND STUDY CALENDAR**

We will collect basic demographic data and screen for delirium using the CAM-ICU (which is standard practice in the ICU). The ABCDEF bundle and CAM-ICU screening tool are performed by the ICU nurses on a daily basis in the morning. The CAM-ICU may be performed later on in the day if the patient's mental status changes. The findings in the ABCDEF bundle and CAM-ICU screening tool are communicated to the ICU team on morning rounds. In patients who develop delirium, we will

collect data on their total ICU/hospital LOS (length of stay), days on mechanical ventilation (if applicable), duration of delirium, and in-hospital mortality.

No additional laboratory studies or investigative studies will be performed for the study.

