## **10.0 CRITERIA FOR EVALUATION AND ENDPOINT DEFINITIONS**

Primary outcome: incidence of delirium, defined by a positive CAM-ICU.

Secondary outcomes: delirium duration, ICU/hospital length of stay, in-hospital mortality, and mechanical ventilation duration.

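### Length of stay and ventilation days are compared with no rule for deaths, so a mortality difference alone can bias both comparisons

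*Combined protocol and SAP*

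**What the plan says.** Section 13.0 gives three separate analyses. For stay: "The length of stay will be compared by truncated negative binomial regression". For ventilation (MV): "Differences in the duration of delirium and MV between the intervention and control groups will be analyzed by analysis of variance (ANOVA"). For death: "while mortality rates will be compared via logistic regression". The truncation point is not given.

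Section 10.0 defines these outcomes by name only: "Secondary outcomes: delirium duration, ICU/hospital length of stay, in-hospital mortality, and mechanical ventilation duration". It gives no start, stop, window or rule for death, and Sections 3.0 and 12 add none. The only sensitivity analysis, propensity weighting in Section 13.0, addresses the lack of randomisation.

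The secondary hypothesis in Section 2.0 is that the intervention will "decrease ICU and hospital length of stay, decrease mechanical ventilation duration, and decrease in-hospital mortality compared to the standard care group".

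Section 9.0 says that, in patients who develop delirium, the study will "collect data on their total ICU/hospital LOS (length of stay), days on mechanical ventilation (if applicable), duration of delirium, and in-hospital mortality". Sections 3.0 and 12 list the same outcomes without that restriction.

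**The concern.** ICU stay, hospital stay and ventilation each have two possible endings, one good (discharge alive, extubation) and one bad (death). A model for the number of days sees only the length. A patient who dies soon after enrolment then contributes the same small number as one who recovers quickly. Neither truncation nor ANOVA tells the two apart, and weighting for baseline covariates does not change how a death is scored.

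The plan expects mortality to differ between the groups. If it does, part of any difference in stay or ventilation reflects who died and not how fast patients recovered. A survival benefit can then appear as longer stay, and excess deaths as shorter stay.

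**Working it through.** **The plan's own figures.** The plan gives no figure for stay, ventilation or study mortality, so there is none to reproduce on this point. Its interval of 8% to 42% for the difference in delirium incidence does reproduce: 0.25 ± 1.96 × √(0.40×0.60/47 + 0.15×0.85/47) = 7.7% to 42.3%. It has no bearing here.

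**Model (assumption).** Let patients leave alive at a constant daily rate *h*, equal in both groups, so that the intervention has no effect on recovery. Let them die at a constant daily rate *k*. Then:

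- mortality *m* = *k*/(*h*+*k*)
- mean stay = 1/(*h*+*k*) = (1−*m*)/*h*
- ratio of mean stays, intervention to control = (1−*m*I)/(1−*m*C)

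The rate *h* cancels, so the ratio depends only on the two mortalities. Ventilation follows the same formula with extubation in place of discharge. No separate figures were worked for ventilation or ICU stay.

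**Results.** All rates are assumptions. The first three rows use *h* = 0.10 per day with *k* = 0.01, 0.02 or 0.04; the others use *h* = 1/14 per day.

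| Mortality, control → intervention | Mean stay, days | Ratio |
|---|---|---|
| 17% → 29% | 8.33 → 7.14 | 0.86 |
| 29% → 17% | 7.14 → 8.33 | 1.17 |
| 17% → 9% | 8.33 → 9.09 | 1.09 |
| 33% → 25% | 9.4 → 10.5 | 1.12 |
| 25% → 16% | 10.5 → 11.8 | 1.12 |
| 16% → 8% | 11.8 → 12.9 | 1.10 |
| 10% → 5% | 12.6 → 13.3 | 1.06 |
| 25% → 33% | 10.5 → 9.4 | 0.89 |

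The shift is about 6% to 17% in size, with no change in recovery in any row. If mortality is low it nearly vanishes: 1% falling to 0% gives 1/0.99 = 1.01.

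**What a competing-risks analysis shows.** Discharge alive by day 28 is *h*/(*h*+*k*) × (1 − exp(−28(*h*+*k*))). In the first row this is 0.833 × (1 − exp(−3.36)) = 80% in controls and 0.714 × (1 − exp(−3.92)) = 70% with the intervention. Mean stay looked better with the intervention; the share leaving alive is worse. The cause-specific discharge hazard ratio is 1.0 in every row, so by itself it would not show the 80% against 70%.

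**Does the direction always hold?** Under constant rates, those who die and those who survive within a group have the same expected stay. A different structure fixes the two means. Take 14 days for survivors and mortality falling from 25% to 16%:

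- deaths at 7 days: 0.25×7 + 0.75×14 = 12.25 against 0.16×7 + 0.84×14 = 12.88 (+0.63 days)
- deaths at 14 days: no difference
- deaths at 18 days: 15.00 against 14.64 (−0.36 days)

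The sign can therefore reverse.

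**How often it would show at 52 per group.** In 20,000 simulated trials (*h* = 1/14, stays rounded up to whole days, a Welch-type comparison of means standing in for the planned regression), mortality differences of 8 to 9 points gave the lower-mortality group the longer mean stay in about 68% to 72% of trials. The stay was significantly longer in about 6% to 8%, against 2.5% expected by chance.

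**How many deaths.** Section 1.0 cites in-hospital mortality of 25% to 33% and ICU mortality of 1% to 16%, both for patients with delirium. Applied to all 52 in a group, these give 13 to 17 and about 1 to 8 deaths. With the 40% delirium incidence in Section 13.0, about 0.40 × 52 = 21 controls develop delirium, and 25% to 33% of them is 5 to 7 deaths. No rate is given for patients without delirium.

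**The case against.** A reader might infer that the plan counts death as a short stay. The documents do not say so; they are silent. All-patient analysis is the plainer reading, since no exclusion is given, but a survivors-only analysis fits the same words. That would not rescue the plan: it conditions on an outcome the intervention is expected to change.

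A reader might also infer that a fall in mortality must lengthen stay, so that the secondary hypotheses contradict each other. This is not supported. Faster recovery could outweigh the bias, the sign can reverse as shown above, and in a pilot of this size the distortion would seldom reach significance.

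Nor is harm to survival hidden. In-hospital mortality has its own comparison, so a shorter stay produced by deaths would be reported beside more deaths. Section 13.0 also justifies the pilot's size by feasibility, base delirium incidence and the effect on delirium, not by stay or ventilation. These objections limit the weight of the point. They do not supply the missing rule, and a separate mortality result does not tell the reader how much of a difference in stay comes from deaths.

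**Conclusion.** The point holds as a gap with a predictable mechanism. The plan names models for days of stay and ventilation, does not separate the two endings, and expects one of them, death, to change. If days are analysed as observed, a mortality difference alone moves mean stay by roughly 6% to 17% under constant rates, equal recovery and the mortality pairs tabulated. The size rests on those assumptions, because the documents give no mortality for the study population and the 25% to 33% applies to patients with delirium. The bias is material only if mortality is substantial and differs between groups, and its direction depends on how long patients who die stay. These are secondary outcomes of a pilot; the change is a cheap improvement worth making.

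**What to change.** In Sections 10.0 and 13.0:

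- **Stay.** Make the main analyses time from enrolment to ICU discharge alive and to hospital discharge alive, with death as a competing event. Report cumulative incidence by group with a subdistribution hazard ratio, and the cause-specific discharge hazard as a supplement. Present both beside mortality.
- **Ventilation.** Analyse ventilator-free days over a fixed, prespecified window (for example 28 days, which is an assumption and not in the documents), with deaths scored 0, by a rank-based comparison. State the convention for patients discharged alive before the window ends; counting them as ventilator-free afterwards avoids further follow-up.
- **Raw days.** Keep days of stay and ventilation as descriptive summaries, split by survivors and deaths.
- **Population.** Reconcile Section 9.0, which reads as collecting these outcomes only in patients who develop delirium, with Sections 3.0 and 12. Such a restriction would itself select on the primary outcome.

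The cost is wording plus a few chart dates: hospital admission, enrolment, ventilation start and stop, and discharge or death. The listed variables do not fix these. They include days from ICU admission to enrolment, but not from hospital admission, and total ventilation days do not show when ventilation occurred. The results will be less direct to read than mean days.
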